### **XIII. Inclusion/Exclusion Criteria:**

Inclusion criteria for primary participants (PP): age  $\geq$  50 years, a diagnosis of dementia (preferably AD) by their neurologist, English language fluency, caregiver consent, and no contraindications for MRI.

Inclusion criteria for caregivers (CG): current provision of care to PP and ability to answer questions about the PP's behaviors, quality of life, and their own level of stress.

Exclusion criteria for PP: lack of assent to study procedures, contraindications for MRI, terminal illness (i.e., life expectancy  $< 1$  year), started dementia medication (i.e., cholinesterase inhibitor or memantine) in the past 3 months or planning to start new dementia medication, current participation in another research study that could potentially confound current study (e.g., medication or behavioral intervention).

Exclusion criteria for CG: major neurological or psychiatric condition, terminal illness, evidence of cognitive impairment or inability to consent to study procedures.

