### II. Currently Available Dementia Treatments

All legally marketed treatments for AD are pharmacological. There are currently 3 pharmacological ligands available with FDA-approved indications for use as treatments of moderate to severe dementia of the Alzheimer's type: donepezil (23mg QD, PO), rivastigmine (13.3mg QD, transdermal patch), and memantine (10 mg BID or 28mg/day QD extended release, PO). Additionally, a combination of donepezil and memantine is available as a single capsule formulation named Namzaric.

Two of these ligands, donepezil and rivastigmine, have their mechanisms of action through non-competitive inhibition of cholinesterases, the enzymes responsible for the hydrolysis of choline esters (Deardorff, Feen et al. 2015). Donepezil is a reversible inhibitor of acetylcholinesterase, the enzyme predominantly responsible for the breakdown of the neurotransmitter acetylcholine, while rivastigmine is a pseudo-irreversible inhibitor of acetylcholinesterase and butylcholinesterase, which plays a minimal role centrally compared to acetylcholinesterase. The neurotransmitter acetylcholine is well-established to play a critical role in learning and memory (Hasselmo 2006). Several deficits in the cholinergic system

have been identified in post-mortem brain examinations of AD (Ferreira-Vieira, Guimaraes et al. 2016), and these ligands are capable of reducing the cognitive and functional deficits experienced by moderate to severe AD patients (Farlow, Salloway et al. 2010; Farlow, Grossberg et al. 2013).

The third ligand, memantine, has its mechanism of action through the anti-competitive antagonism of glutamatergic N-methyl-D-aspartate (NMDA) receptors (Chen and Lipton 1997) across the brain as well as having neuroprotective effects (Hardingham and Bading 2010). Memantine has also been demonstrated to reduce cognitive and functional deficits experienced by moderate to severe AD patients, even when already receiving donepezil (Reisberg, Doody et al. 2003; Tariot, Farlow et al. 2004; Grossberg, Manes et al. 2013).

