### **III. Limitations of Currently Available Dementia Treatments**

Though several compounds are under clinical investigation for delaying or preventing the progression from the stage of mild cognitive impairment to AD, there have been no successful trials for over 15 years. All FDA-approved therapies for the treatment of AD produce symptomatic improvement only. Though the pharmacotherapies described above are highly valuable in this patient population, there remains a significant need for treatments for long term symptomatic improvement and disease-modifying potential, particularly therapies that can be used in combination with current pharmacotherapeutic options.

Finally, the number of patients experiencing adverse events is considerable, particularly with the cholinesterase inhibitors. In the pivotal trial of 23mg/day donepezil for moderate to severe AD, 74% of patients experienced at least one adverse reaction to the medication with 19% of patients discontinuing the medication for this reason (Farlow, Salloway et al. 2010). The most common adverse reactions included nausea (12%), vomiting (9%), diarrhea (8%), anorexia (5%), and dizziness (5%). In the pivotal trial of 13.3mg/day rivastigmine for severe AD, 75% of patients experienced at least one adverse reaction to the medication with 26% of patients discontinuing the medication for this reason (Farlow, Grossberg et al. 2013). The most common adverse reactions included erythema at application site (13%), agitation (12%), urinary tract infection (8%), dermatitis at application site (8%), and falls (8%). Thus there exists a large proportion of the moderate to severe AD population for whom acetylcholinesterase inhibitors are not an option, as can be seen in the high discontinuation rates (19% and 26%) due to side effects in the two clinical trials.

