**XIX. Monitoring.** To encourage adherence to the home-treatment PBM regimen, study research staff will call CGs every two weeks to "check-in" on how the treatments are going. The Daily Home Treatment Journals will be reviewed during these calls. In addition to monitoring adherence, clinical safety, and any adverse events, factors that might affect study outcomes including changes in medications, caregivers, or medical conditions will also be assessed during the "check-in" calls. CGs will be also asked about any changes to the PP's health status since the last contact "check-in" call, including any emergency room visits, hospitalizations, or injuries. Events that are serious and unexpected will be reported to the UCSF IRB within 5 working days. Co-interventions also will be assessed during the "check in" calls using a standardized questionnaire that asks about any changes since last contact that might affect study outcomes including changes in medications, caregivers, medical conditions, usual activities or other factors.

**XX. Risks and Benefits:** There are some potential risks associated with the study. Potential risks associated with undergoing a MRI include: 1) metal flying into the MRI scanner, 2) minimal discomfort associated with lying supine for MRI scans, 3) possible claustrophobia when lying in the scanner, and 4) possible annoyance due to excessive noise produced by the MRI. We will minimize these risk by doing the following: 1 ) risk of metal flying into the MRI will be minimized by careful screening of the subject and by the use of a metal detector that is just outside the door leading into the MRI room, 2) discomfort from laying supine in the MRI scanner will be minimized with padding, pillows, and blankets to make the subject as comfortable as possible, 3) subjects will have voice contact with the MR and technician throughout the MRI scan and may be removed from the MR scanner at any time upon their request, 4) noise will be reduced by earplugs and noise reducing head phones. Risks to confidentiality will be minimized as described above.

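### The dementia-drug exclusion covers only starts, so patients with a recent or planned stop or dose change are eligible; this adds noise at 5 per arm and can distort the unrandomised analyses in either direction

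*Combined protocol and SAP*

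**What the plan says.** The protocol's section XIII (Inclusion/Exclusion Criteria) excludes a primary participant who has "started dementia medication (i.e., cholinesterase inhibitor or memantine) in the past 3 months or planning to start new dementia medication". The look-back for starts is 3 months; the planned-start limb has no end date.

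The only other exclusion that touches medication is "current participation in another research study that could potentially confound current study (e.g., medication or behavioral intervention", which concerns other research studies and not ordinary clinical care. Besides age, the inclusion criteria in XIII ask for "a diagnosis of dementia (preferably AD) by their neurologist, English language fluency, caregiver consent, and no contraindications for MRI", with no stable-dose requirement. The criteria in the Protocol Summary add none.

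On what the drugs do, background section II states that "these ligands are capable of reducing the cognitive and functional deficits experienced by moderate to severe AD patients". Section XIX (Monitoring) says that at the two-weekly calls "factors that might affect study outcomes including changes in medications, caregivers, or medical conditions will also be assessed".

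**The concern.** A 3-month look-back on starts makes sense only if a drug effect that has not settled could distort the outcomes. The same reasoning applies to a stop or a dose change, and the protocol gives no reason for covering one kind of change and not the others. The background says the drugs act on cognition and function, cognition is the outcome of hypothesis 1, and section XIX itself names medication changes as something that might affect outcomes.

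With 5 patients per arm, one patient whose cognition is moving for a drug-related reason carries a fifth of the weight in an arm mean. Two analyses under Statistical Methodology in the Protocol Summary are also made within one arm and so gain nothing from randomisation. These are the Delayed group's Cohen d (baseline to week 12, then week 12 to week 24) and the Spearman correlations in the Immediate group.

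**Working it through.** **1. Apply the clause literally.**

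| Patient | Started in past 3 months? | Planning to start a new drug? | Result |
|---|---|---|---|
| Long-term user, dose changed two weeks before baseline | No | No | Eligible |
| Long-term user, drug stopped two weeks before baseline | No | No | Eligible |
| Long-term user, stop or dose change already planned for week 4 | No | No | Eligible |
| Switched to a different dementia drug two weeks before baseline | Yes | – | Excluded |

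**2. Look for a later safeguard.** The telephone screen (XI) collects basic medical history, but no criterion acts on a stop or dose change. The baseline assessments listed in XIV include no record of drug or dose. Randomisation (XV) states no stratification. The calls in XIX ask about changes since the last contact, so they are not designed to find a change made before baseline. They are introduced with "To encourage adherence to the home-treatment PBM regimen, study research staff will call CGs every two weeks", and the text does not say whether the Delayed group is called while it waits. The SAP has no medication covariate, sensitivity analysis or handling rule.

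**3. Inputs for the size.** From section X: 10 dyads, 5 per arm, with the number set by funding; there is no power figure to reproduce. Assumed, because the documents do not give them: k, the number of affected patients, 1 to 4; c, the drug-related change in one patient, 1 to 5 scale points or 0.5 to 1.5 SD of the change score; two-sided alpha 0.05.

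**4. Chance imbalance.** The probability that a of the k affected patients fall in a given arm is C(k,a)·C(10−k,5−a)/C(10,5), with C(10,5) = 252.
- k = 1: always 1 v 0.
- k = 2: both in one arm, 2·C(8,3)/252 = 112/252 = 0.444.
- k = 3: 3 v 0, 2·C(7,2)/252 = 42/252 = 0.167; otherwise 2 v 1, 0.833.
- k = 4: unequal, (12 + 120)/252 = 0.524.

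**5. Shift in the between-group difference.** Shift = net imbalance × c/5. For a net one patient and c = 1 to 5 points: 0.2 to 1.0 points. For a net two: 0.4 to 2.0 points. In SD units, one patient with c = 1 SD shifts the difference by 0.2 SD. The standard error at 5 v 5 is √(2/5) = 0.632 SD, so this is 0.2/0.632 = 0.32 of a standard error.

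**6. Does the t-test keep its size?** Simulation, 200,000 runs, no PBM effect, affected patients allocated at random:

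| k | c (SD) | Rejection rate |
|---|---|---|
| 1 | 1.5 | 0.0491 |
| 2 | 1.0 | 0.0496 |
| 2 | 1.5 | 0.0491 |
| 3 | 1.5 | 0.0506 |

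It does. If two affected patients are fixed in the same arm, the rate is 0.055, 0.068 and 0.084 for c = 0.5, 1.0 and 1.5 SD. With one it stays near 0.05. For changes that precede randomisation, those unlucky allocations are already averaged into the table above.

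**7. Room for extra noise.** By the noncentral t with 8 df and noncentrality d·√(5/2), power at 5 per arm is 0.286 for d = 1, 0.549 for d = 1.5 and 0.791 for d = 2.0. Only a very large effect is detectable even without added variance.

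**8. Unrandomised analyses.** In the Delayed group, if decline after a recent stop falls before week 12, it lands in the untreated period and makes the PBM period look better by contrast. If benefit from a recent dose change falls there, the PBM period looks worse. In the Immediate-group correlations, one affected patient is one of five ranks.

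**The case against.** A reader might infer that drug change is confounded with the PBM effect in the randomised comparisons. The documents do not support that. Section XIV puts baseline assessment before randomisation, so a change made before baseline, or already planned by then, is independent of arm, and step 6 shows that the test keeps its size. The higher rejection rates need changes concentrated in one arm. That could arise systematically only after entry, and this clause does not govern unplanned changes made then.

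A reader might also apply the background's discontinuation figures ("19% of patients discontinuing the medication for this reason" for donepezil, 26% for rivastigmine) to these ten patients and conclude that stops are common. Those are stops for adverse reactions during trials of particular strengths. They are not rates of stopping before entry, or of planned stops, in patients established on a drug, and no dose-change rate is given at all.

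It is also fair to say that any trait held by one patient in ten is unbalanced, that section X calls this a pilot, proof-of-concept study and makes no power claim, and that the Delayed-group effect sizes are estimates rather than hypothesis tests and do not appear in the SAP text. No passage says how quickly a stop or dose change acts, so its timing relative to week 12 is an assumption. These points limit the consequence. They do not close the gap in the wording: stops and dose changes are admitted, and nothing later catches or adjusts for them.

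**Conclusion.** The gap is certain from the text; its effect is modest and cannot be fixed from the documents. For the randomised tests there is no systematic bias. The cost is added variance and chance imbalance: c/5 per net affected patient, or 0.2 to 1.0 points for an assumed c of 1 to 5, and a 44% chance that two affected patients share an arm. For the Delayed group's within-group effect sizes and the Immediate-group correlations, distortion is possible in either direction, with no randomisation to offset it. All magnitudes rest on assumed k and c, and the rejection rates also on an assumed two-sided 0.05. The change is worth making because it completes a rule the protocol already has at very little cost.

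**What to change.** In XIII, replace the clause with: *started, stopped or changed the dose of a cholinesterase inhibitor or memantine in the 3 months before baseline, or planning to start a new dementia medication, or a stop or dose change already planned before the Week 24 assessment*. Ask about it at the telephone screen in XI.

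The planned-start limb should stay without an end date. Ending it at Week 12 would newly admit a patient who intends to start a drug in weeks 12 to 24, which is the Delayed group's PBM period. The limb on planned stops and dose changes runs to Week 24 because the Delayed-group effect sizes use that period.

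This is an eligibility rule only. It does not restrict what treating physicians do after entry; such changes continue to be recorded under XIX, and how the analysis handles them is a separate question that this wording does not settle. The cost is one sentence, one screening question, and a few candidates deferred until 3 months have passed or excluded.

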### **XIV. Study Procedures:**

Baseline Psychometric Assessment (with PP and CG separately). The baseline assessment will take place after the consent visit and prior to randomization. PPs and CGs will be assessed separately so that their answers do not influence each other. PPs will be directly assessed by research staff while CGs will be

provided with self-administered forms when feasible or may complete the assessment in person, by phone or mail-in.

Baseline Assessments in PPs:

- Cognitive function (Montreal Cognitive Assessment MOCA). Cognitive function will be measured using the Montreal Cognitive Assessment, MOCA). The MOCA's score range is the same as the MMSE (0–30), but has additional, more complex tasks including executive function. Items address orientation, drawing figures, processing speed, naming objects, memory, recall, attention, vigilance, repetition, verbal fluency, and abstraction.
- Alzheimer's Disease Assessment Scale -- Cognitive Subscale (ADAS-cog). Cognitive function will also be assessed with the ADAS-cog, one of the most commonly used outcome measures in dementia drug treatment trials and one of the measures considered by the Food and Drug Administration (FDA) for approval of dementia medications. It includes direct assessment of learning (10-word list), naming (objects), following commands, constructional praxis (figure copying), ideational praxis (mailing a letter), orientation (person, time, place), recognition memory and remembering test instructions. The ADAS-cog is scored on an 80-point scale, with higher scores reflecting worse cognitive function.
- Quality of life (Quality of Life Scale in Alzheimer's Disease, QOL-AD). The Quality of Life Scale in Alzheimer's Disease (QOL-AD) is a standard quality of life measure that asks parallel questions of affected individuals and caregivers and was used in our pilot study. Current quality of life is rated as poor (1 point), fair (2 points), good (3 points) or excellent (4 points) in 13 areas: physical health, energy, mood, living situation, memory, family, marriage, friends, self as a whole, ability to do chores around the house, ability to do things for fun, money, and life as a whole. Scores may range from 13 to 52 with higher scores reflecting better quality of life. Prior studies have found that the QOL-AD is a valid and reliable measure, with Cronbach's alpha of 0.84 for patient reports and 0.86 for caregiver reports and interrater reliability based on Cohen's kappa values >0.70.

Baseline Assessments in CGs:

- Caregiver burden (Caregiver Burden Inventory, CBI). The Caregiver Burden Inventory (CBI) is a standard measure that includes 24 items and 5 domains. Caregivers are asked to rate how often each statement describes their feelings (never, rarely, sometimes, quite frequently, nearly always). The total score may range from 0 to 96 with higher scores reflecting greater feelings of burden. The CBI has good internal consistency (Cronbach's alpha, 0.73-0.86), and it was sensitive to change in our pilot study.
- Participant quality of life (QOL-AD). As described above, the QOL-AD is a standard quality of life measure that asks parallel questions of affected individuals and caregivers and was used in our pilot study.
- Neuropsychiatric Inventory (NPI). Caregivers will also complete the NPI, which assesses the frequency, severity and level of distress caused by 12 common dementia-related behaviors (delusions, hallucinations, agitation/aggression, depression/dysphoria, anxiety, elation/euphoria, apathy/indifference, disinhibition, irritability/lability, aberrant motor behavior, sleep and appetite/eating). The NPI has good test-retest reliability (0.79-0.86) and good internal consistency (Cronbach's alpha, 0.87-0.88).
- Positive Aspects of Caregiving Scale is a standard measure that asks caregivers to rate their agreement/disagreement with 11 statements about positive aspects of caregiving on a 5-point Likert scale (disagree a lot ... agree a lot).

- Geriatric Depression Scale (GDS) short form assesses depressive symptoms in caregivers based on self-report. The GDS short form is a 15-item yes/no scale that is valid in people with and without dementia

Follow-Up Psychometric Assessments (PPs and CGs separately). Follow-up assessments will be performed at weeks 6,12, 18, and 24 for all PPs and CGs. The procedures and measures will be identical to those at baseline.

Baseline and follow-up neuroimaging measures: Neuroimaging outcome measures will be acquired from PPs at baseline and week 12 on a research dedicated 3T Siemens Skyra at the San Francisco VA Medical Center. The following scans will be acquired at baseline and the post-treatment on a research-dedicated Siemens 3 Tesla Skyra MRI scanner at the SF VAMC: (1) T1-weighted 3D whole brain gradient echo MRI: TR/TE/TI = 2400/2.14/1000 ms, 1x1x1 mm^3 resolution, with fat suppression; (2) bandwidth matched variable flip angle spin echo T2-weighted 3D whole brain SPACE (Sampling Perfection with Application optimized Contrasts using different flip angle Evolution) MRI TR/TE 3200/565 ms, 1x1x1 mm^3 resolution, without fat suppression. (3) T2-weighted fluid attenuated inversion recovery (FLAIR) for optimal segmentation of white matter lesions: TR/TE/TI = 6000/355/2200 ms, 1x1x1 mm^3 resolution, We will use prospective motion correction by Kineticor on the T1, T2, and FLAIR images. (3) Whole-brain task-free resting-state fMRI: T2\*-weighted gradient echo-echo planar sequence with 2.5 x 2.5 x 3 mm^3 resolution and TR/TE = 3000/30 ms. Subjects will be instructed to keep their eyes open. (4) Arterial-spin labeled (ASL) perfusion MRI will be acquired with a 2D pulsed ASL (pASL) sequence using the Siemens product PICORE PASL sequence with the Q2TIPs technique for defining the spin bolus: TR/TE = 3400/12 ms, TI1/TI = 700/1900 ms, field of view (FOV) = 256 mm, 24 sequential 4-mm-thick slices with a 25% gap between the adjacent slices, partial Fourier factor = 6/8, bandwidth = 2368 Hz/px, and imaging matrix = 64 x 64. The first volume of the 105 ASL acquisitions will be used as the M0 image; the remaining 104 volumes will be used as 52 control-label pairs. Subjects will be instructed to keep their eyes open during the ASL scans. The total scan time is approximately 45 minutes, the same scan duration as the Alzheimer's Disease Neuroimaging Initiative (ADNI) imaging protocol on the Siemens MRI scanner. In our experience, even older individuals with dementia can remain in the MRI scanner with minimal movement for this amount of time. Moreover, we have developed a protocol where we invite the participants' caregivers to accompany them into the MRI scan room to alleviate any potential anxiety, which further reduces motion-related artifacts.

**XV. Randomization:** Dyads of PP and CGs be randomized into one of two groups. The Immediate PBM Group will begin treatment with the Vielight Neuro device upon completion of baseline assessments. Treatment will continue for at least 12 weeks. *Because results from Saltmarche et al. pilot study suggest that cognitive gains achieved by patients with dementia may not be maintained without continued PBM treatment, PPs/CGs randomized to the Immediate PBM group will have the option of continuing PBM treatment after completion of Week 12 assessments.* The Delayed PBM Group will not begin treatment with the Vielight Neuro device until after completion of week 12 assessments.

**XVI. Caregiver Device Training** -- Prior to starting the PBM treatments, the CG will be trained how to position the Vielight Neuro device on the PP, how to control, how to clean, and how to maintain the Vielight Neuro device in a single 30 minute session. This training session will either take place at the SF VAMC or at the location of the PP/CG's choice (e.g., their home).

**XVII. Treatment Diary/Log:** To encourage adherence to the home-treatment PBM regimen, CGs will be instructed to log each treatment in the "Daily Home Treatment Journal." CGs will also be instructed to

note changes in the participants' memory, other cognitive processes, and general health conditions in the journal, which will be reviewed at bi-monthly "check-in" calls with the research staff.

**XVIII. Confirmation of Correct Device Use** -- After the first week of treatment, a research staff member will confirm that the CG knows how to properly use and maintain the Vieelight Neuro device. During the "confirmation" appointment, the CG will be asked to demonstrate his/her understanding and ability to correctly place the device on the PP. Any errors will be noted by the study staff and the caregiver will be re-trained or corrected as necessary. The research study staff will also review the treatment diary with the CG to check treatment compliance and its recording. The CG and PP will be encouraged to ask any questions or provide comments on device use which will be noted by study staff.

**XIX. Monitoring.** To encourage adherence to the home-treatment PBM regimen, study research staff will call CGs every two weeks to "check-in" on how the treatments are going. The Daily Home Treatment Journals will be reviewed during these calls. In addition to monitoring adherence, clinical safety, and any adverse events, factors that might affect study outcomes including changes in medications, caregivers, or medical conditions will also be assessed during the "check-in" calls. CGs will be also asked about any changes to the PP's health status since the last contact "check-in" call, including any emergency room visits, hospitalizations, or injuries. Events that are serious and unexpected will be reported to the UCSF IRB within 5 working days. Co-interventions also will be assessed during the "check in" calls using a standardized questionnaire that asks about any changes since last contact that might affect study outcomes including changes in medications, caregivers, medical conditions, usual activities or other factors.

**XX. Risks and Benefits:** There are some potential risks associated with the study. Potential risks associated with undergoing a MRI include: 1) metal flying into the MRI scanner, 2) minimal discomfort associated with lying supine for MRI scans, 3) possible claustrophobia when lying in the scanner, and 4) possible annoyance due to excessive noise produced by the MRI. We will minimize these risk by doing the following: 1 ) risk of metal flying into the MRI will be minimized by careful screening of the subject and by the use of a metal detector that is just outside the door leading into the MRI room, 2) discomfort from laying supine in the MRI scanner will be minimized with padding, pillows, and blankets to make the subject as comfortable as possible, 3) subjects will have voice contact with the MR and technician throughout the MRI scan and may be removed from the MR scanner at any time upon their request, 4) noise will be reduced by earplugs and noise reducing head phones. Risks to confidentiality will be minimized as described above.

Risks associated with the baseline or follow-up assessments include psychological or emotional distressing. This risk will minimized by having research staff who administer baseline and follow-up assessments be carefully trained using standard procedures on strategies for working with individuals with dementia and their CG in a sensitive and respectful manner. PP and CG will not be forced to answer any questions. Staff will be trained to recognize and appropriately address signs of discomfort or stress when indicated (e.g., by taking breaks, rescheduling appointment, skipping sections that cause undue discomfort). PP will have the option to choose between private viewing (available only to research staff, auditors, and monitoring committee) or private/public viewing (available to private viewers and also public, such as being included in the training video, study website, and/or presentations).

The research is justified because the risks to subjects are very low and the knowledge that could be gained from the study may aid with development and implementation of therapies that enhance brain function and quality of life in individuals with dementia.

**XXI. Compensation Method:** PP and CG will not be paid for study participation. However, because the Saltmarche et al. pilot study suggests that cognitive gains achieved by individuals with dementia are not maintained without continued PBM treatment, we feel it would be unethical to take back the PBM devices after the study. Therefore, PPs will be offered the opportunity to keep and to continue using their Vielight Neuro devices once they complete all study procedures.

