MRI assessments. Five PP will be randomized to a "Delayed PMB" group that will not start treatment with the Vielight Neuro device until after the 12-week psychometric and MRI assessment. Cognitive function and quality of life will be assessed in all PPs at baseline, weeks 6, 12, 18, and 24. Caregiver burden, positive aspects of caregiving, depressive symptomology, and dementia-related behaviors in the PP will be assessed in all CGs at baseline, weeks 6, 12, 18, and 24. Neuroimaging measures will only be assessed in PPs at baseline and week 12.

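### Does the plan leave the Delayed arm without routine event collection before week 12?

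*Combined protocol and SAP*

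**What the plan says.** Section XIX states: "To encourage adherence to the home-treatment PBM regimen, study research staff will call CGs every two weeks to" check in on progress with treatment. It adds: "The Daily Home Treatment Journals will be reviewed during these calls". The same calls cover safety and adverse events, emergency visits, hospital admissions and injuries, and changes in medication, caregiver or medical condition. A standardised co-intervention questionnaire "asks about any changes since last contact that might affect study outcomes". No arm, first week or last week is given.

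Section XV says: "The Delayed PBM Group will not begin treatment with the Vielight Neuro device until after completion of week 12 assessments". Section XVII says "CGs will be instructed to log each treatment in the" home journal, "which will be reviewed at bi-monthly" calls.

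The psychometric schedule is explicit about both arms. Section VII says that the caregiver measures "will be assessed in all CGs at baseline, weeks 6, 12, 18, and 24", and Section XIV says: "Follow-up assessments will be performed at weeks 6,12, 18, and 24 for all PPs and CGs". Section XXII obliges the investigator to report adverse events to the IRB, but does not describe how they are collected.

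**The concern.** The purpose given for the calls is adherence, and journal review is part of them. Before week 12 neither applies to a Delayed dyad. Where the protocol means everyone it sometimes says so, as in the assessment schedule, whereas Section XIX speaks only of caregivers. Section XVII uses the same unqualified term for logging treatments, which only treating caregivers can do. A reader could infer that calls begin when treatment begins.

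Baseline to week 12 is the only randomised comparison. If the control arm were not called in that period, adverse events, medication changes and co-interventions could not be compared between arms when the week-12 results are read. Staff contact would also differ by arm, while burden, depressive symptoms and the NPI are caregiver reports. With 5 dyads per arm, one unrecorded medication change would affect a fifth of an arm (1/5 = 20%).

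**Working it through.** The plan states no figure for the number of calls, so there is nothing to reproduce. The check is a contact count under each reading, then a comparison of the texts.

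**Inputs.** Call interval 2 weeks (Section XIX); randomised period 12 weeks and Delayed start after week 12 (Section XV); 5 dyads per arm, 10 in all (Section X).

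**Count.**
- Calls per dyad by week 12: 12 / 2 = 6 (weeks 2, 4, 6, 8, 10, 12), or 5 if the last is merged with the week-12 visit.
- Calls follow treatment: Immediate 5 × 6 = 30; Delayed 5 × 0 = 0.
- All caregivers called: 30 and 30.
- Randomised follow-up: 10 × 12 = 120 dyad-weeks, of which Delayed 5 × 12 = 60; 60 / 120 = 50%. This share only restates that half the dyads are controls.
- Look-back if calls follow treatment and Delayed treatment starts straight after week 12: first Delayed call at about week 12 + 2 = 14, so up to 14 weeks of recall against 2.

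**Which reading does the text support?**
1. *The unqualified term.* Section XIV also uses it, without the word all, for the baseline assessment. That takes place before randomisation, so every caregiver has it. The missing word in Section XIX therefore shows nothing.
2. *Content.* Section XVII is limited by its object, the logging of treatments. Most of Section XIX is not: hospital admissions, injuries, medication, change of caregiver and usual activities occur with or without a device. Questions about factors that could affect outcomes are most useful when both arms answer them.
3. *Look-back.* The co-intervention questionnaire refers to the last contact, which a week-12 visit might reset. The health-status question refers to the last check-in call. A Delayed dyad not yet called would have no such call, so the visit would not cut off weeks 0 to 12 for hospital and emergency events.
4. *Other contacts.* Staff assess participants in both arms directly at weeks 6 and 12, and both arms have a week-12 MRI with safety screening. None of this is described as event collection, but Delayed dyads are not out of contact. The device confirmation visit is tied to the first week of treatment. Training is dated only as before treatment starts, so Delayed training by week 12 is not ruled out.
5. *Use of the data.* The Statistical Methodology in the Protocol Summary and the SAP cover cognition, NPI, connectivity, blood flow, correlations, caregiver scales and within-Delayed effect sizes. No planned test takes adverse events, medication changes or co-interventions as input.

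**Interval wording.** Section XVII's term for the calls can mean twice a month, which agrees with Section XIX. Read as every two months, it would put only about one call in the 12 weeks. Section XIX gives the interval in plain words, so this is an editorial slip.

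**The case for a change.** The strongest case for a change is that no other visible route would fill the gap. The measures listed for weeks 6 and 12 contain no adverse-event, medication or co-intervention item, and caregivers may complete theirs by form, phone or mail. The journal is a treatment journal read at the same calls. The IRB reporting clock starts only when the investigator learns of an event. Data not collected in weeks 0 to 12 cannot be reliably recovered later. The Protocol Summary also plans effect sizes within the Delayed group for weeks 0–12 and 12–24; if calls began with treatment, contact and treatment would change together at week 12. Making the wording explicit would cost at most about 6 × 5 = 30 short calls.

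Much of this stands: Section XIX is silent on arm and start, and the calls are the only routine collection described. But each consequence depends on the narrower reading, which the text does not state and which most of the call's content does not favour. If all caregivers are called, only wording is at issue. It also remains possible that the study-flow figure, which is not shown, or removed text gives the timing of the calls.

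**Conclusion.** The concern identifies an unwritten detail, not a rule that gives a wrong result. Calling every caregiver every two weeks and asking the treatment questions only of those who are treating fits Section XIX as it stands. It is also how a sensible study team would fill the gap. On that reading contact by call is equal, 6 against 6 per dyad, with no dyad-weeks uncovered. The contrast of 6 against 0 arises only if staff tie the calls to treatment, which the documents never say.

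Even then, no planned test would use the missing data directly. Any effect would be on interpretation, through unequal contact and unrecorded co-interventions, and neither its direction nor its size can be derived from the documents. This assumes a two-week interval, 5 dyads per arm and Delayed treatment starting straight after week 12. For a 10-dyad pilot described as proof of concept, who is called and from when belongs in the working call schedule. No change to the protocol or SAP follows.
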